The primary objective of this study is to evaluate AFO efficacy in children with spastic CP on the ICF components 'body functions and structures' (i.e. biomechanics of gait) and 'activities and participation' (i.e. walking efficiency and frequency of participation).

The main research question related to this objective is: 1) what are the effects of wearing a specific AFO on biomechanics of gait, walking efficiency, daily activity and frequency of participation in children with spastic CP, whose gait is characterized by a flexed knee pattern? An additional research question is: 1a) what biomechanical changes of gait, resulting from wearing the AFO, lead to an improved walking efficiency, increased daily activity and/or frequency of participation in this specific patient group?

Secondary objective:

The secondary aim of this study is to identify prognostic factors for either a successful or unsuccessful outcome of AFO treatment on activities and participation (i.e. walking efficiency, daily activity and frequency of participation) in children with spastic CP.

The main research question for this objective is: 2) can we identify prognostic factors for a successful or unsuccessful outcome on walking efficiency, daily activity and frequency of participation after AFO treatment in children with spastic CP, whose gait is characterized by flexed knee pattern? Additional questions are: 2a) how do AFO properties (e.g. stiffness) influence the patient's gait biomechanics?; and 2b) what is the effect of gait improvements, as a result of AFO stiffness optimization, on daily activity and frequency of participation?

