3.1.1 Data collection and study planning

After enrolling the study (recruitment), baseline measurements (T0) will be performed for the subject, walking with shoes only. Additional measurements will be performed for the subject's current AFO (if applicable). Then, for each subject a new AFO will be prescribed, of which stiffness (K) will be varied into three configurations: rigid, stiff, and flexible (further explained in chapter 5). A balanced block randomization will be applied for six possible sequences of AFO stiffness configurations. Each AFO configuration will be worn for an acclimation period of four to eight weeks, after which AFO efficacy will be evaluated (T1_{k1}

 $,T1_{K2}$ and $T1_{K3}$). An analysis the evaluation of all AFO configurations will lead to selection of the stiffness that results in the most favourable effects for a particular subject, referred to as the subject's optimal AFO. This optimal AFO will be worn for twelve to twenty weeks, after which a second set of follow-up measurements ($T2_{Kopt}$) will be done for the selected optimal AFO (figure 1).

Baseline measurements (T0) will have total duration of 4.5 hour. To limit the burden for the subject, baseline testing will be equally sub-divided into three measurement moments: $T0_{cast}$, $T0_{fit}$, and $T0_{deliver}$ (respectively representing the regular consultancies of casting, fitting and delivery of the new AFO).

The evaluation of AFO efficacy will be done for each configuration, and is referred to as $T1_{k1}$, $T1_{K2}$ and $T1_{K3}$ which represent, dependent on the randomization, either a rigid, stiff or flexible configuration. These measurement moments will last approximately three hours each. Subsequent analysis of these measurements will lead to selection of the subject's optimal AFO. Follow-up measurements for the optimal AFO ($T2_{kopt}$) will be done after wearing the orthosis for twelve to twenty weeks. This broad range of long-term follow-up time is included in the study design, since a child's daily activity and participation will be dependent on environmental factors, such as weather circumstances (e.g. temperature). Measurements at $T2_{kopt}$ will have duration of approximately three hours.

Additional (outside lab) measurements will be performed during baseline (T0_{deliver}), evaluation (T1_{κ}) and follow-up (T2_{kopt}) measurements (table 1).

| Measurement moment | | | Location | Duration |

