The rigid configuration of the Neuro Swing[®] system will not allow any dorsal or plantar flexion during walking, while the stiff and flexible configuration of the Neuro Swing[®] system will. For stiff configuration, the ankle joint system will be equipped with the spring that best approaches the stiffness of the subject's baseline AFO. For the flexible configuration, the system will be equipped with a spring that is less stiff (if the spring of the stiff configuration is the "fifth" (strongest), the flexible AFO will be configured with the "fourth" spring of the Neuro Swing[®] package).

Tuning

To further ensure fair comparison of AFO efficacy of different configurations, tuning of AFO-footwear combination (AFO-FC) should be done adequately and similarly for each AFO configuration. Tuning involves modification of the alignment of the AFO-FC in order to optimize gait kinetics and kinematics (64). The position of lower limb segments is described relative to the force of gravity, which acts vertically. The angle of the segment relative to the vertical, referred to as shank to vertical angle (SVA), can be expressed in degrees of incline or recline from the vertical (65). Most efficient gait is assumed to be achieved with a optimal SVA in midstance, which should be 10-12° inclined. Owen (65) recently introduced a clinical algorithm for the design and tuning of AFO-FCs, aiming to achieve the most optimal SVA. By using this algorithm for each AFO prescription, it is assumed that tuning of each AFO-FC will be adequate and for each AFO configuration.

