Baseline measurements with intervention AFO (visit IV, V, and VI)

During the period that the AFO configuration is worn, subjects will also wear the SAM for one week. After wearing the first intervention AFO-FC, subjects will come to the medical center for the evaluation measurements (T1_K). During this visit, 3D-gait analysis and ECWT will be performed, and the FMS and FAQ will be completed. The researcher will ask both the child and parent(s) to rate the worn AFO in terms of satisfaction. Then, properties of the new AFO configuration will be determined and the second AFO-FC will be tuned. Only during visit IV (T1K1), a 3D-gait analysis with the new configuration (K2) will be performed directly,to measure the immediate biomechanical effects of the AFO. The subject will wear the second AFO-FC for four to eight weeks (acclimation period will be matched according to total time that the first AFO-FC is worn), after which the same evaluation measurements will be done (including SAM). The motivation diary will be kept until the next visit to the medical center. This time schedule and set of measurements will be repeated for the third AFO-FC.

Optimal AFO selection (visit VI)

When the short-term follow-up measurements for all AFO configurations are completed, data will be analyzed and the subject's most optimal AFO will be selected. Selection of the subject's optimal AFO will be based on data of gait analysis (primarily on the knee angle in midstance), ECWT, and degree of satisfaction of the child and parent(s). Subsequently, the

Neuro Swing[®] ankle joint system of the subject's AFO-FC will be configured according to what is considered as optimal.

Long-term follow-up measurements (visit VIII)

The subject will wear the optimal AFO-FC during a period of twelve to twenty weeks, to ensure full habitation before long-term follow-up measurements will be performed ($T2_{kopt}$). Measurements at $T2_{kopt}$ will include the CAPE and SAM (of which data will be assessed during the week prior to the visit), adherence (data with the @monitor (83) will be assessed two weeks prior to the visit), 3D-gait analysis, ECWT, FAQ, FMS, and GAS.

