3.6.3 Multivariate analysis

Evaluation of efficacy of the subject's optimal AFO will be based on analyses of pre/postintervention differences in primary and secondary outcome measures. Means of baseline measurements (T0) will be compared to evaluation measurements (T1_K) and long-term follow-up measurements (T2_{Kopt}) using a Linear Mixed Model (LMM) for repeated measures¹.

Multivariate linear regression analyses will be applied to investigate what changes in the secondary outcome measure 'biomechanics of gait' are associated with changes in primary outcome measures 'walking efficiency' and 'daily activity'. First, a stepwise univariate regression (ANOVA) will be performed to determine which factors are significantly associated with changes in biomechanics of gait. Next, significant factors will be analysed in a multivariate regression analysis model.

Multivariate regression analysis will also be applied to investigate to what extent the child characteristics and AFO properties provide determinants for success of treatment with AFOs. First, a stepwise univariate regression (ANOVA) will be performed to determine which factors are significantly associated with outcome of AFO treatment. Significant factors will be inculded in a multivariate regression model. Factors that will be analysed in the model will include baseline motor impairements, GMFCS level, gait pattern, EC of walking, physical fitness level, and AFO stiffness and neutral anlge.

¹ Participation measures (assessed with the CAPE) will only be done at baseline (T0) and at long-term follow-up (T2). Assuming that data are normally distributed, means of this outcome measure will be compared using paired samples t-test.

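### The prognostic regression lists AFO stiffness and neutral angle as determinants of success, but under the optimal AFO stiffness was chosen from the child's own response, so its coefficient is not a stiffness effect

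*Protocol*

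**What the plan says.** - **Analysis.** Section 3.6.3 will examine "to what extent the child characteristics and AFO properties provide determinants for success of treatment with AFOs". Factors are screened one at a time and the significant ones go into a joint regression. The candidates include "gait pattern, EC of walking, physical fitness level, and AFO stiffness", with neutral angle. No visit is named for the outcome and no term for the child is mentioned.
- **Question served.** The secondary objective asks: "can we identify prognostic factors for a successful or unsuccessful outcome on walking efficiency, daily activity and frequency of participation".
- **How the final stiffness arises.** Section 3.1.1 describes "selection of the stiffness that results in the most favourable effects for a particular subject". Section 3.5.1 (optimal AFO selection) says the choice "will be based on data of gait analysis (primarily on the knee angle in midstance), ECWT, and degree of satisfaction" of child and parents.
- **How the levels arise.** Under section 3.3, for the stiff configuration "the ankle joint system will be equipped with the spring that best approaches the stiffness" of the AFO the child already had. The flexible one uses a weaker spring.
- **Randomised part.** Each child wears all three configurations in a block-randomised order (section 3.1.1). Section 3.6.2 compares their T1 means by repeated measures ANOVA.
- **Timing.** Participation (CAPE) is measured at T0 and T2 only (Table 2 and the footnote to section 3.6.3). Energy cost, step activity and AFO properties are measured at each T1 visit and at T2.

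**The concern.** A factor chosen because of how the child responded differs in kind from GMFCS level or fitness, which are fixed before treatment. If children with more severe gait problems tend to do best in a stiffer AFO, and also gain less, selected stiffness will be associated with poor outcome even where stiffness has no average effect. Energy cost sharpens this, because it is both a selection criterion and a primary outcome.

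The springs also follow the child before any selection, since the stiff level copies the earlier prescription. Appendix A allows the neutral angle to be changed in answer to gait complaints, so that factor depends on response too.

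At stake is the interpretation. The introduction wants the determinants to feed an evidence-based framework for AFO management. A stiffness determinant from this model could be read as advice on stiffness when it only records which children ended up with which spring.

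**Working it through.** **1. The plan's own figure.** The protocol gives no number for this regression. The only related one is the sample size: N = 2 × 1.70² × (1.96 + 0.84)² / 1.26² = 28.6, rounded up to 29, which reproduces. The 32 to be enrolled is used below as n. The figure has no other bearing on the point.

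**2. Which visit?** Setting the passages side by side:
- T2 is suggested by the opening of section 3.6.3, which concerns the optimal AFO, and by an ordinary regression, which implies one row per child.
- T1 is not excluded: energy cost, step activity and AFO properties all exist there, and the mixed-model sentence just before covers both T1 and T2.
- For participation only T2 is possible, so stiffness is the selected one.
- If T1 rows are used, each child gives three correlated rows that an ordinary regression treats as independent.

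The stated model needs correcting on either reading.

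**3. Size under selection, by simulation. All inputs are assumptions; none comes from the protocol except n = 32.**
- Severity S is standard normal. Stiffness k is -1, 0 or 1. The child's optimum is a × S.
- Gain = -0.5 S - c (k - aS)², plus noise with SD 0.5 at each visit.
- The level with the best observed T1 gain is selected. T2 gain is then related to the selected k.
- The average loss from stiffness is c (k² + a²), equal at k = -1 and k = 1. The average linear effect is therefore zero; the middle level is better by c.

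| a | c | mean correlation | p < 0.05, unadjusted |
|---|---|---|---|
| 0.5 | 0.1 | -0.14 | 12% |
| 0.5 | 0.3 | -0.32 | 45% |
| 1 | 0.1 | -0.25 | 29% |
| 1 | 0.3 | -0.45 | 75% |

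Repeat runs put the top value at up to about 77%. Limits and adjustment:
- If the optimum does not track severity (a = 0), or severity does not affect gain, the rate is about 5%.
- With severity in the model, the rate is about 5-7% if it is measured without error, 6-13% at reliability 0.8 and 7-37% at reliability 0.5.
- The within-child T1 contrast of the two extreme levels stays at about 5% throughout.

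**4. Direction and size of bias, second simulation** (assumed between-child SD 1.2, error SD 0.6, lower outcome better).

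| Assumed truth | True mean slope | Slope on selected stiffness | Within-child T1 slope |
|---|---|---|---|
| Child slopes vary at random | -0.40 | -0.30 | -0.40 |
| Response tied to severity | +0.40 | +1.22 | +0.40 |
| Zero mean effect | 0 | about 0 | about 0 |
| Symmetric child-specific optimum | 0 | about 0 | about 0 |

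The selected-stiffness slope runs from attenuated to about three times too large (1.22 / 0.40 = 3.05). The randomised contrast is right in every row.

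**The case against.** - **T2 is nowhere stated, and the layout may sit in a SAP that is not at hand.** This stands as a limit: the protocol does not fix a T2 model with one row per child. It does not remove the point, because the factor list itself is stated, and for participation only T2 exists.
- **The stiffness question already has a randomised analysis.** This stands. A reader might infer that the trial cannot show how stiffness acts. The protocol does not support that: the question "how do AFO properties (e.g. stiffness) influence the patient's gait biomechanics" is answered on average by section 3.6.2, as are the average effects on energy cost and daily activity. That ANOVA does not, however, test which children benefit from which stiffness.
- **The aim is prognostic, so an association is enough.** This stands in part. Selected stiffness may be described. But it is known only after the child's response has been seen, so it cannot serve as a baseline predictor, and calling it a determinant invites a causal reading.
- **Adjustment removes most of the inflation.** This is true where severity is well measured. A reader might take 12-77% as the error rate of the final model; it is that of the screening step under assumed tracking. The screen still decides which factors enter.
- **Selection need not place each child at a true optimum.** This stands. Knee angle leads the choice and long-term outcomes do not enter it. The argument needs only that the choice depends on response.

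**Conclusion.** The point holds in a limited form. Wherever the outcome is taken under the optimal AFO, the stiffness coefficient in the section 3.6.3 prognostic regression combines any stiffness effect with the reasons for the choice, and the documents give no means of separating the two. On a T1 reading, the fault is instead the neglected clustering within child.

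The size is uncertain. It runs from no inflation, if the optimum does not track severity, to a screen that flags stiffness in about three trials in four. Adjustment brings this to between about 5% and 37%, depending on how well severity is measured. Every one of these figures rests on assumed inputs. Tracking is nevertheless plausible on the protocol's own terms, since the introduction cites evidence that AFO properties and patient characteristics have an optimal match.

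Only the claim that stiffness (and, for related reasons, neutral angle) is a determinant of success is affected. The primary comparisons and the average T1 stiffness comparison are not. As a secondary-objective matter with an inexpensive remedy, it lies between worth considering and should be changed.

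**What to change.** In section 3.6.3:
1. Name the outcome visit for the prognostic regression. In the T2 model keep only child characteristics measured at baseline.
2. Estimate stiffness from the T1 data, up to 32 × 3 = 96 observations, with a mixed model that has a child effect, measured stiffness centred within child, and wearing period. Add a few stiffness-by-baseline terms chosen in advance; these address which child benefits from which stiffness.
3. Report any T2 association with stiffness or neutral angle as a description of what was selected.

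This costs wording and a re-specified model on data already planned, with no extra visits or children. The price is that T2 stiffness can no longer be reported as a determinant of long-term success. Participation, absent at T1, will have no stiffness estimate, and the interaction terms will be imprecise with 32 children.

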4. SAFETY REPORTING

4.1 Section 10 WMO event

In accordance to section 10, subsection 1, of the WMO, the investigator will inform the subjects and the reviewing accredited METC if anything occurs, on the basis of which it appears that the disadvantages of participation may be significantly greater than was foreseen in the research proposal. The study will be suspended pending further review by the accredited METC, except insofar as suspension would jeopardise the subjects' health. The investigator will take care that all subjects are kept informed.

4.2 Adverse and serious adverse events

Adverse events are defined as any undesirable experience occurring to a subject during the study, whether or not considered related to the experimental treatment. All adverse events reported spontaneously by the subject or observed by the investigator or his staff will be recorded.

All serious adverse events (SAEs) will be reported through the web portal *ToetsingOnline* to the accredited METC that approved the protocol, within 15 days after the sponsor has first knowledge of the serious adverse reactions.

SAEs that result in death or are life threatening should be reported expedited. The expedited reporting will occur not later than 7 days after the responsible investigator has first knowledge of the adverse reaction. This is for a preliminary report with another 8 days for completion of the report.

4.3 Follow-up of adverse events

All adverse events will be followed until they have abated, or until a stable situation has been reached. Depending on the event, follow up may require additional tests or medical procedures as indicated, and/or referral to the orthotist or a medical specialist (rehabilitation physician). A detailed description of the precautions that will be taken to prevent the occurrence of adverse events related to the intervention is provided in Appendix A. Additionally, a flow chart of the policy for handling complaints is provided, which will be used in case of an adverse event.

5. ETHICAL CONSIDERATIONS

5.1 Regulation statement

This study will be conducted according to the principles of the Declaration of Helsinki (version 2008) and in accordance with the Medical Research Involving Human Subjects Act (WMO).

5.2 Recruitment and consent

Subjects will be recruited from the patient population of the VUmc (Amsterdam, the Netherlands). Subjects will be informed about the study and are invited to participate by a letter, which will be send out by the medical center. After receiving the letter, sufficient time will be given before subjects are asked to consent. When subjects agree to participation, child and parents are asked to fill in a written informed consent.

5.3 Benefits and risks assessment, group relatedness

AFOs are commonly prescribed in order to improve mobility in children with CP. However, a clear concept for AFO treatment in relation to prescription goals is missing and therefore, the decision-making process of AFO prescription primarily relies on current best available evidence and expert experience. This implicates that AFO treatment is not always as adequate as possible. This study aims to improve AFO management in the (near) future in order to achieve most adequate AFO treatment in CP and results of the study might be beneficial for the subject's AFO treatment. This study only enrols patients who are already using AFOs for one year or longer. Consequently, patients are not asked to participate in an additional therapy on top of their regular medical program.

Patients will enrol the study at the moment they are indicated to get new AFOs. As described, measurement moments are scheduled simultaneously with regular consultancies as much as possible, therewith limiting the number of visits to the medical center. Subjects will have also to visit the medical center for measurements after delivery of the new AFO, implicating greater burden compared to usual care. However, these measurement moments are included in the study design to enable selection of the subject's optimal AFO, implicating the possibility of a more beneficial AFO treatment compared to their usual care. Consequently, the subject might experience direct benefits of his or her new AFO.

Since the intervention AFO will be custom made, it is assumed that the orthosis will not cause greater burden or more pain compared to a conventional AFO. Measurements of the study are non-invasive. Markers, sensors and cables might somehow increase the burden during the measurements compared to normal walking and fatigue or pain might occur. However, the risk of pain will be minimal and subjects can quit the measurements if pain

occurs. Subjects might get fatigued during some of the measurements (e.g. fitness tests). The researcher will therefore ensure that the subjects and parent(s) are completely informed before starting the measurements and subjects will get sufficient time to recover from all tests.

We believe that the benefits of this study clearly outweigh the risks or burdens for the subjects.

5.4 Compensation for injury

Insurance for the subjects participating in the study (in Dutch):

Ingevolge art. 7 van de Wet medisch -wetenschappelijk onderzoek met mensen (Staatsblad 1998, 161) is door de verrichter van het onderzoek, het VUmc, een verzekering afgesloten die de door het onderzoek veroorzaakte schade door dood of letsel van de deelnemende proefpersonen dekt. Deze verzekering is afgesloten bij Onderlinge Waarborgmaatschappij Centramed, [name]. De verzekering voldoet aan de bepalingen van het Besluit verplichte verzekering bij medisch-wetenschappelijk onderzoek met mensen (Stbl. 2003, 266). Aan het onderzoek deelnemende proefpersonen zullen schriftelijk worden geïnformeerd over de verzekering.

Liability insurance sponsor/investigator

The sponsor/investigator has a liability insurance which is in accordance with article 7, subsection 6 of the WMO.

The sponsor (also) has an insurance which is in accordance with the legal requirements in the Netherlands (Article 7 WMO and the Measure regarding Compulsory Insurance for Clinical Research in Humans of 23th June 2003). This insurance provides cover for damage to research subjects through injury or death caused by the study.

- € 450.000,-- (i.e. four hundred and fifty thousand Euro) for death or injury for each subject who participates in the Research;
- € 3.500.000,-- (i.e. three million five hundred thousand Euro) for death or injury for all subjects who participate in the Research;
- 3. € 5.000.000,-- (i.e. five million Euro) for the total damage incurred by the organisation for all damage disclosed by scientific research for the Sponsor as 'verrichter' in the meaning of said Act in each year of insurance coverage.

The insurance applies to the damage that becomes apparent during the study or within four years after the end of the study.

